## Analysis Plan

### F.2 Aim 1 analyses:

*Hypothesis 1a:* As compared to the control group, clinicians randomized to the intervention will have a **greater mean number objective measures of communication quality** in encounters with both Black and White patients combined and in each race subgroup.

The goal of the primary Hypothesis (1a) is to determine the efficacy of the clinician communication coaching intervention versus usual care on an objective measure of the quality of communication from baseline to post-training. Additionally, we are interested the intervention effect within Black patients and White patients separately. The quality of communication will be assessed at both baseline encounters and post-training encounters by a summary of clinician encounter counts derived from the audio recordings. We plan to use mixed-effects models as our primary analytic strategy because they will appropriately account for the intracluster correlation of multiple patient encounters for each clinician. The mixed-effects model for Hypothesis 1a will have the following form:

$\log(\mu_{ik}) = \mu_0 + \mu_1(int) + \mu_2(premean_k) + \mu_3(clinsex_k) + \mu_4(clintype_k) + b_{0k}$ , where  $Y_{ik}$  is the number of quality communication statements for patient  $i$  in the post-period clustered within physician  $k$ , and  $Y_{ik}$  is assumed to be Poisson with mean and variance equal to  $\mu_{ik}$ . The fixed effects in the model include indicator variables intervention group (*int*), each clinician's mean number of quality communication statements per conversation prior to the intervention, and the clinician stratification variables. The random intercept,  $b_{0k}$ , is normally distributed and accounts for dependence of encounters within clinicians. PROC GLIMMIX (with the quadrature option) in SAS (SAS Inc., Cary, NC) will be used to fit the mixed-effects Poisson model and test the primary hypothesis (1a). Specifically, if  $\mu_1$  is positive and significantly different than zero, this provides evidence of greater communication quality among patients and clinicians in the intervention group as compared to the control group.

The analysis for Hypothesis 1a will also be conducted for encounters with white and black patients separately.

*Hypothesis 1b:* Black patients and White patients seen by clinicians in the intervention group will report **higher mean quality of patient-centered care** compared to patients seen by control group clinicians.

The secondary outcome, quality of patient-centered care, is a continuous measure assessed at baseline and post-training. However this is a patient-centered outcome (i.e., the patient's perception) and the same patients are not being followed longitudinally. Therefore, the patients' data collected in the baseline period will not be incorporated in the analysis.

$Y_{ik} = \mu_0 + \mu_1(int) + \mu_3(clinsex_k) + \mu_4(clintype_k) + b_{0k}$ , where  $Y_{ik}$  is the IPC score for patient  $i$  clustered within physician  $k$ , and  $Y_{ik}$  is assumed to be normally distributed. The fixed effects in the model include indicator variables intervention group (*int*) and the clinician stratification variables. The random intercept,  $b_{0k}$ , is normally distributed and accounts for dependence of patients within clinicians. PROC MIXED in SAS (SAS Inc., Cary, NC) will be used to fit the mixed-effects model and test hypothesis (1b). Specifically, if  $\mu_1$  is positive and significantly different than zero, this provides evidence of greater IPC among patients of clinicians in the intervention group as compared to the control group.

Hypothesis 1b will be repeated within Black and White patients separately with the goal to ensure that the intervention is effective in each subgroup (as an overall treatment effect can sometimes mask important heterogeneity). Relative differences in the intervention effect on reducing disparities will be addressed in Aim 2.

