REACH P2: Communication Coaching to Improve Patient and Clinician Satisfaction in Cardiology Encounters

NCT Number: NCT03464110

Date: 12.14.18

Protocol Title Communication Coaching to Improve Patient and Clinician Satisfaction in Cardiology Encounters

Purpose of the study

Aim 1: Determine the effect of a clinician communication coaching intervention versus control on an objective measure of the quality of communication (primary outcome) and patients' perceptions of the quality of patient-centered care (secondary outcome), both overall and within Black and White patients.

Hypothesis 1a: As compared to the control group, the intervention will improve objective measures of communication quality in encounters with both Black and White patients combined and in each race subgroup.

Hypothesis 1b: Black patients and White patients seen by clinicians in the intervention group will report improvements in the quality of patient-centered care compared to patients seen by control group clinicians.

Aim 2: Determine the effect of a clinician communication coaching intervention versus control on racial disparities in objective measures of communication quality (primary outcome) and in the quality of patient-centered care (secondary outcome).

Hypothesis 2a: Racial disparities in objective measures of communication quality will be reduced in encounters with clinicians in the intervention group as compared to encounters with control group clinicians.

Hypothesis 2b: Racial disparities in patients' perceptions of the quality of patient-centered care (IPC score) will be reduced among those having encounters with clinicians in the intervention group as compared to encounters with clinicians in the control group.

Research Abstract

We propose to conduct a cluster randomized controlled trial of a clinician communication coaching intervention in ambulatory cardiology practices. The aim is to determine the effect of a clinician communication coaching intervention versus control on an objective measure of the quality of communication and patients' perceptions of the quality of patient-centered care, both overall and within Black and White patients. We will recruit cardiology clinicians and randomly assign them to the intervention or control arms. We will enroll their adult patients pre-intervention and post-intervention

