F.4 Missing Data: The survey data may contain missing values in any of the clinician-level and patient-level variables due to drop-out, a missed interim assessment, or item non-response. In addition, there may be a rare instance of audio-recorder mechanical failure or of clinicians or patients turning off the recorder in the middle of the encounter. Our primary analysis technique, hierarchical models, allow for unbalanced or incomplete data and will be fit with maximum-likelihood methods to preserve the missing at random assumption. Additionally, we will thoroughly explore reasons for dropout, and depending upon the type and scope of missing data, variables may be multiply imputed as recommended by Panel on Handling Missing Data in Clinical Trials.²⁸ Note that if needed, we will utilize imputation methods that account for the multiple types of correlation inherent in the clustered data structure.

F.5 Power and Sample Size Considerations: The effect of interest for Aims 1 and 2 pre-post relative difference between the intervention and usual care groups; Aim 1 focuses on the overall difference and the difference within Black and White patients separately, while Aim 2 on the difference within Black patients compared to White patients. The sample size requirements are greatest for Aim 2; as discussed by Leon and Heo (2009), the needed sample size for the patient race-by-intervention group interaction is 4 times that needed for the overall test. For Hypotheses 1a and 2a, our sample size calculations are based upon the difference between two Poisson rates (incident rate ratio) in a cluster randomized design (i.e., patients clustered within clinician). Note that we are not explicitly accounting for the additional clinician-time correlation, so these calculations are conservative. Based on preliminary studies, the baseline mean number of quality communication statements is 1.0, and a conservative range of coefficients of variation (CV) is 0.2 to 0.5 to account for patients clustered within clinician. With a sample size of 240 patients (6 per clinician) and a type-I error of 5%, we will have 80% power to detect incident rate ratios of 1.5 to 1.8 for Hypothesis 1a in the overall test, 1.6 to 1.9 for Black or White patients separately, and 1.8 to 2.1 for Hypothesis 2a.

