For hypotheses 1b and 2b, our sample size calculations are based upon the difference between two means in a cluster randomized design. Again, we are not explicitly accounting for the additional clinician-time correlation, so these calculations are conservative. We present a conservative range of intraclass correlation coefficients (ICC) to account for patients clustered within clinician. With a sample size of 240 patients (6 per clinician) and a type-I error of 5%, we will have 80% power to detect mean differences of effect size 0.37 to 0.44 for Hypothesis 1b in the overall test, 0.52 to 0.56 for Black or White patients separately, and 0.65 to 0.91 for Hypothesis 2b. PASS 15 was used for all calculations.

We plan to enroll approximately 2 clinicians per month and approximately 17 patients per month over 2 years.

Data & Safety Monitoring

The quality of data collection will be enhanced through extensive training of all personnel involved in data collection, with on-going quality assessments conducted while the project is in the field. Quality control checks will include feedback on protocol fidelity, interpersonal skills, and data entry and cleaning. We will also work with an experienced database manager who will oversee the operations, reconcile data from the various sources, conduct data quality assurance, provide reports to the study team, and conduct routine basic data analyses under the supervision of the study statistician. Reconciling differences in data reported from various sources will be on a case-by-case basis, ongoing as data is collected.

Privacy, Data Storage & Confidentiality

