### F.3 Aim 2 Analyses:

*Hypothesis 2a:* Racial disparities in objective measures of the quality of communication will be **lower** in encounters with clinicians in the intervention group as compared to encounters with clinicians in the control group.

*Hypothesis 2b:* Racial disparities in patients' perceptions of the quality of patient-centered care will be **lower** among those seen by clinicians in the intervention group as compared to encounters with clinicians in the control group.

A mixed-effects Poisson model will again be the primary modeling strategy for the objective communication outcome Aim 2 analyses. For this Aim, however, the model will include patientrace interaction terms and will have the following form:  $\log(\lambda_{ik}) = \lambda_0 + \lambda_1(\text{Black}_i) + \lambda_2(\text{int}_k) + \lambda_3(\text{Black}_i * \text{int}_k) + \lambda_4(\text{premean}_k) + \lambda_5(\text{clinsex}_k) + \lambda_6(\text{clintype}_k) + b_{0k}$ , where  $Y_{ijk}$  is the number of quality communication statements for patient  $i$  in the post-period clustered within physician  $k$ , and  $Y_{ik}$  is assumed to be Poisson with mean and variance equal to  $\lambda_{ik}$ . Again, the random intercept  $b_{0k}$  is normally distributed and account for dependence of encounters within clinicians. In this model,  $\text{Black}_i$  is the indicator variable for whether a patient is Black (value of 1) or White (value of 0).

Post-treatment, the Black-white mean difference among patients seen by usual care group clinicians is  $BW_{uc} = \exp(\lambda_0 + \lambda_1) - \exp(\lambda_0)$ , **this represents the racial disparity in communication quality**. The B-W mean difference among patients seen by intervention group clinicians is  $BW_{int} = \exp(\lambda_0 + \lambda_1 + \lambda_2 + \lambda_3) - \exp(\lambda_0 + \lambda_2)$ .

Hypothesis 2a will be tested by  $\lambda_5$  being significantly greater than zero, indicating a greater mean number of quality communication statements for the intervention group versus the control group for Black patients as compared to White patients (i.e., the intervention group reducing the racial disparity). The estimated incident rate ratio, p-value, and 95% confidence intervals will be calculated via estimate statements in PROC GLIMMIX.

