A similar linear mixed-effects model (rather than a Poisson) model will be used to examine the reduction in racial disparities of quality of patient-centered care and test Hypothesis 2b. Note that in a linear model framework, the coefficients will represent differences in means rather than rate ratios.

Power and Sample Size Considerations: The effect of interest for Aims 1 and 2 is the relative difference in the post-period between the intervention and usual care groups; Aim 1 focuses on the overall difference and the difference within Black and White patients separately, while Aim 2 on the difference within Black patients compared to White patients. The sample size requirements are greatest for Aim 2; as discussed by Leon and Heo (2009), the needed

sample size for the patient race-by-intervention group interaction is 4 times that needed for the overall test. For Hypotheses 1a and 2a, our sample size calculations are based upon the difference between two Poisson rates (incident rate ratio) in a cluster randomized design (i.e., patients clustered within clinician).

Based on preliminary studies, the baseline mean number of quality communication statements is 1.0, and a conservative range of coefficients of variation (CV) is 0.2 to 0.5 to account for patients clustered within clinician. With a **sample size of 240 patients in the post period (6 per clinician)** and a type-I error of 5%, we will have 80% power to detect incident rate ratios of 1.5 to 1.8 for Hypothesis 1a in the overall test, 1.6 to 1.9 for Black or White patients separately, and 1.8 to 2.5 for Hypothesis 2a.

For hypotheses 1b and 2b, our sample size calculations are based upon the difference between two means in a cluster randomized design. We present a conservative range of intraclass correlation coefficients (ICC) to account for patients clustered within clinician. With a **sample size of 240 patients (6 per clinician)** and a type-I error of 5%, we will have 80% power to detect mean differences of effect size 0.37 to 0.44 for Hypothesis 1b in the overall test, 0.52 to 0.56 for Black or White patients separately, and 0.65 to 0.91 for Hypothesis 2b. PASS 15 was used for all calculations.

	Number of clinicians	Number of patients in the postintervention phase (number per clinician)	Hypothesis 1a and 2a: Incident Rate Ratio		Hypothesis 1b and 2b: Mean Effect Size	
			CV	Pre-post Relative Rate	ICC	Pre-post Difference

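### Does the pre-post wording around the IPC outcome leave the analysis of Hypotheses 1b and 2b unsettled?

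*SAP*

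**What the plan says.** **Hypothesis 1b.** In SAP F.2, and in the same words in the Protocol's data analysis section, the IPC patients' "data collected in the baseline period will not be incorporated in the analysis". The reason given is that different patients are seen in the two periods. The printed linear mixed model has arm, clinician sex, clinician type and a clinician random intercept. It has no period term and no baseline term.

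**Pre-post language elsewhere.**
- Protocol, Purpose of the study: patients of intervention clinicians "will report improvements in the quality of patient-centered care compared to patients seen by control group clinicians".
- Protocol F.5: "The effect of interest for Aims 1 and 2 pre-post relative difference between the intervention and usual care groups". For Hypotheses 1b and 2b it adds: "Again, we are not explicitly accounting for the additional clinician-time correlation, so these calculations are conservative".
- SAP, Power and Sample Size Considerations: "The effect of interest for Aims 1 and 2 is the relative difference in the post-period". The IPC column of the table that follows is nevertheless headed "Pre-post Difference", and the count-outcome column beside it carries a similar pre-post label.

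**Hypothesis 2b.** Both documents say only that "A similar linear mixed-effects model (rather than a Poisson) model will be used". The model it resembles is that for 2a, introduced in SAP F.3 by "the model will include patientrace interaction terms and will have the following form". The SAP's 2a model contains each clinician's pre-intervention mean. The Protocol's 2a model has time terms over both periods.

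**The concern.** The printed 1b model estimates a difference between arms in the post-period. A pre-post effect is a different quantity, with a different variance. Baseline rests on only 4 patients per clinician, so a literal between-arm difference in change would be much less precise than the post-period difference. If the 80% power claim referred to that contrast, it would be badly wrong. The sentence calling the figures conservative invites a similar misreading: a one-period model has no clinician-time correlation to leave out, so no reserve comes from that source.

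For 2b, an analyst could carry over the time terms, a baseline mean or nothing, and claim in each case to follow the plan. For a named hypothesis, that is room for choice after the data are seen.

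**Working it through.** **1. Do the tabulated IPC figures belong to the post-period analysis?**

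Inputs: 20 clinicians per arm; 6 post-period patients per clinician overall and 3 in a race subgroup; ICC 0.01, 0.05, 0.10 (SAP power table); two-sided 5% (Protocol, general considerations); 80% power; SD 1.

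Detectable effect = (1.96 + 0.84) × √(2 × DE / (20m)), with DE = 1 + (m − 1) × ICC.

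Overall, m = 6, DE = 1.05, 1.25, 1.50:
- ICC 0.01: 2.80 × √(2.10/120) = 0.371
- ICC 0.05: 2.80 × √(2.50/120) = 0.404
- ICC 0.10: 2.80 × √(3.00/120) = 0.443

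| | ICC 0.01 | ICC 0.05 | ICC 0.10 |
|---|---|---|---|
| 1b overall, normal | 0.371 | 0.404 | 0.443 |
| 1b overall, t on 238 df | 0.372 | 0.406 | 0.445 |
| SAP table | 0.37 | 0.41 | 0.44 |
| 1b subgroup (m = 3), normal | 0.517 | 0.536 | 0.560 |
| SAP table | 0.52 | 0.54 | 0.56 |
| 2b, m = 2, t on 38 df | 0.646 | 0.659 | 0.674 |
| 2b, m = 1, t on 38 df | 0.909 | 0.909 | 0.909 |
| SAP table | 0.65–0.91 | 0.66–0.91 | 0.67–0.91 |

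Every IPC figure reproduces from post-period patients alone. Normal-approximation power at the tabulated 1b overall values is 79.9%, 81.1% and 79.5%.

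**2. What would a literal pre-post contrast need?**

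With 4 pre and 6 post patients per clinician (Protocol, Design & Procedures), the variance of a clinician's change is [ICC + (1 − ICC)/6] + [ICC + (1 − ICC)/4] − 2 × ICC × r. Here r is the correlation of clinician effects between periods. The documents do not give it, so it is ranged from 0 to 1. At ICC 0.05 and r = 1 the variance is 0.95 × (1/6 + 1/4) = 0.396, and 2.80 × √(2 × 0.396/20) = 0.557.

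| Detectable effect (power at the tabulated value) | ICC 0.01 | ICC 0.05 | ICC 0.10 |
|---|---|---|---|
| r = 1 | 0.569 (45%) | 0.557 (54%) | 0.543 (62%) |
| r = 0.5 | 0.576 (44%) | 0.592 (49%) | 0.611 (52%) |
| r = 0 | 0.583 (43%) | 0.624 (45%) | 0.672 (45%) |

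These figures would matter only if some document specified this contrast, and none does. It requires an arm difference at baseline to be estimated and subtracted. The Protocol's two-period models (1a and 2a) have no arm main effect and no baseline arm-by-race term, so they constrain the arms to be equal at baseline. The SAP models use post-period outcomes only.

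For a linear version of the Protocol's constrained form, simulated variance relative to post-only is 1.000, 0.974 and 0.907 at r = 1, and 1.003, 0.996 and 0.982 at r = 0.5 (8,000 trials per setting). Using baseline IPC that way would save 0 to 9% of variance.

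**3. Does the unwritten 2b model matter?**

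Race varies within clinician, so the race-by-arm term is estimated mainly from Black-White differences inside each clinician's own patients. A clinician-level covariate largely cancels from those differences. Two readings were simulated against a post-only model without baseline (race probability 0.5 per patient, variance components known):
- Adding a clinician pre-period mean (r = 1; 1,500 trials per ICC): variance ratio 1.005, 0.995, 0.986. The estimate shifts by an SD of 0.067, 0.093 and 0.128 standard errors.
- Using the Protocol's two-period form (r = 1 or 0.5; 600 trials per setting): variance ratio 0.983 to 0.996, shift 0.06 to 0.13 standard errors.

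With 3 Black and 3 White patients per clinician, the post-only contrast needs 2.80 × √(2 × (1 − ICC)(1/3 + 1/3)/20) = 0.720, 0.705 and 0.686. All three lie inside the tabulated ranges.

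**The case for a change.** The best case for a change is that the contradiction lies within each document, so the SAP does not simply supersede the Protocol. The Protocol excludes baseline IPC and then describes its power as pre-post. The SAP corrects its power text but not its table header. A reader who relies on the header could credit the trial with 80% power for a contrast that has about 43 to 62%. The sentence calling the figures conservative has no basis for 1b. With 36 clinician-level degrees of freedom, power at the tabulated values is 77.7%, 78.9% and 77.3%. And 2b should have a model on paper.

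The inconsistency stands as a matter of wording, but the rest has little force:
- The header sits in a table whose patient column counts post-intervention patients, below SAP text that gives a post-period effect and a model that can estimate nothing else.
- The Protocol's talk of improvements relative to control patients reads naturally as an ordinary between-arm comparison.
- The 36-df result concerns the choice of degrees of freedom and the rounding of tabulated values, not the use of baseline data.
- The 2b gap is narrow. The exclusion is worded for the outcome, which 2b shares with 1b, although it appears under 1b. The SAP's baseline covariate is defined as a mean count of communication statements, not an IPC score. The natural reading therefore leaves baseline IPC out.

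**Conclusion.** No change to the plan follows. For 1b, the exclusion sentence, the printed model, its test and the power figures agree with one another. The pre-post header, the Protocol's description of the effect and its remark about conservatism are clerical leftovers, and correcting them would alter no result. Excluding baseline IPC is also a fair choice, since the constrained two-period form would cut variance by at most about 9%, and only with ICC 0.10 and fully stable clinician effects.

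For 2b, the missing formula is a gap that analysts would fill sensibly: patient race, arm, their interaction, the clinician stratification variables and a clinician random intercept. The alternatives examined change the variance by less than 2% and move the estimate by about 0.06 to 0.13 standard errors, which would rarely alter a conclusion.

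This rests on the SAP's ICC range, a roughly even race mix within clinicians, and assumed between-period correlations of clinician effects of 0.5 to 1 (1 only for the baseline-mean check).

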### F.3 Aim 2 Analyses:

*Hypothesis 2a:* Racial disparities in objective measures of the quality of communication will be **lower** in encounters with clinicians in the intervention group as compared to encounters with clinicians in the control group.

*Hypothesis 2b:* Racial disparities in patients' perceptions of the quality of patient-centered care will be **lower** among those seen by clinicians in the intervention group as compared to encounters with clinicians in the control group.

A mixed-effects Poisson model will again be the primary modeling strategy for the objective communication outcome Aim 2 analyses. For this Aim, however, the model will include patientrace interaction terms and will have the following form:  $\log(\lambda_{ik}) = \lambda_0 + \lambda_1(\text{Black}_i) + \lambda_2(\text{int}_k) + \lambda_3(\text{Black}_i * \text{int}_k) + \lambda_4(\text{premean}_k) + \lambda_5(\text{clinsex}_k) + \lambda_6(\text{clintype}_k) + b_{0k}$ , where  $Y_{ijk}$  is the number of quality communication statements for patient  $i$  in the post-period clustered within physician  $k$ , and  $Y_{ik}$  is assumed to be Poisson with mean and variance equal to  $\lambda_{ik}$ . Again, the random intercept  $b_{0k}$  is normally distributed and account for dependence of encounters within clinicians. In this model,  $\text{Black}_i$  is the indicator variable for whether a patient is Black (value of 1) or White (value of 0).

Post-treatment, the Black-white mean difference among patients seen by usual care group clinicians is  $BW_{uc} = \exp(\lambda_0 + \lambda_1) - \exp(\lambda_0)$ , **this represents the racial disparity in communication quality**. The B-W mean difference among patients seen by intervention group clinicians is  $BW_{int} = \exp(\lambda_0 + \lambda_1 + \lambda_2 + \lambda_3) - \exp(\lambda_0 + \lambda_2)$ .

Hypothesis 2a will be tested by  $\lambda_5$  being significantly greater than zero, indicating a greater mean number of quality communication statements for the intervention group versus the control group for Black patients as compared to White patients (i.e., the intervention group reducing the racial disparity). The estimated incident rate ratio, p-value, and 95% confidence intervals will be calculated via estimate statements in PROC GLIMMIX.

A similar linear mixed-effects model (rather than a Poisson) model will be used to examine the reduction in racial disparities of quality of patient-centered care and test Hypothesis 2b. Note that in a linear model framework, the coefficients will represent differences in means rather than rate ratios.

Power and Sample Size Considerations: The effect of interest for Aims 1 and 2 is the relative difference in the post-period between the intervention and usual care groups; Aim 1 focuses on the overall difference and the difference within Black and White patients separately, while Aim 2 on the difference within Black patients compared to White patients. The sample size requirements are greatest for Aim 2; as discussed by Leon and Heo (2009), the needed

sample size for the patient race-by-intervention group interaction is 4 times that needed for the overall test. For Hypotheses 1a and 2a, our sample size calculations are based upon the difference between two Poisson rates (incident rate ratio) in a cluster randomized design (i.e., patients clustered within clinician).

Based on preliminary studies, the baseline mean number of quality communication statements is 1.0, and a conservative range of coefficients of variation (CV) is 0.2 to 0.5 to account for patients clustered within clinician. With a **sample size of 240 patients in the post period (6 per clinician)** and a type-I error of 5%, we will have 80% power to detect incident rate ratios of 1.5 to 1.8 for Hypothesis 1a in the overall test, 1.6 to 1.9 for Black or White patients separately, and 1.8 to 2.5 for Hypothesis 2a.

For hypotheses 1b and 2b, our sample size calculations are based upon the difference between two means in a cluster randomized design. We present a conservative range of intraclass correlation coefficients (ICC) to account for patients clustered within clinician. With a **sample size of 240 patients (6 per clinician)** and a type-I error of 5%, we will have 80% power to detect mean differences of effect size 0.37 to 0.44 for Hypothesis 1b in the overall test, 0.52 to 0.56 for Black or White patients separately, and 0.65 to 0.91 for Hypothesis 2b. PASS 15 was used for all calculations.

	Number of clinicians	Number of patients in the postintervention phase (number per clinician)	Hypothesis 1a and 2a: Incident Rate Ratio		Hypothesis 1b and 2b: Mean Effect Size	
			CV	Pre-post Relative Rate	ICC	Pre-post Difference
Aim 1: Overall intervention versus usual care	40 (20 in each treatment arm)	240 (6 per clinician)	0.2 0.35 0.5	1.5 1.6 1.8	0.01 0.05 0.1	0.37 0.41 0.44
Aim 1: Racial subgroup intervention versus usual care	40 (20 in each treatment arm)	120 (3 per clinician)	0.2 0.35 0.5	1.6 1.8 1.9	0.01 0.05 0.1	0.52 0.54 0.56
Aim 2: Racial differences in intervention versus usual care	40 (20 in each treatment arm)	Effective sample size is 60 (1 or 2 per clinician)	0.2 0.35 0.5	1.8-2.2 1.9-2.3 2.1-2.5	0.01 0.05 0.1	0.65-0.91 0.66-0.91 0.67-0.91
